Pregnancy testing will be performed every 4-weeks throughout study enrollment. As in-clinic visits are performed bi-monthly following Visit 4 (Week 12), subjects will perform in-home urine pregnancy tests at Week 16, Week 24, Week 32, Week 40 AND Week 48 and 4-weeks post the final study visit. The test date and result will be documented.

In-home pregnancy testing window is  $\pm$  3 days

Collected pre-dose, when possible.

Includes fasted hematology, serum chemistry, SARS-CoV-2 testing, and lipids performed by the central lab.

At the Week 52 visit, patients will be assessed via SALT for treatment success (Responder) defined as having an absolute SALT score of  $\leq 20$  at Week 52. These responders will be eligible to continue in the OLE extension for up to a maximum of one additional year.

Study drug dispensation will occur at Visit 9 (Week 52) for RESPONDERS ONLY (defined as having a SALT score  $\leq 20$ ).

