4.1. Treatment Group Presentation by Analysis

For analyses of disposition, demographics, baseline characteristics, concomitant medications, and medical history, subjects will be analyzed under their first actual treatment received (8 mg BID or 12 mg BID) in CP543.5002. The following treatment columns will be used:

- CTP-543 8 mg BID
- CTP-543 12 mg BID
- Total CTP-543

Summary tables for the laboratory evaluations, vital signs, and ECGs will include the following treatment columns referring to the starting dose in CP543.5002 and modified dose, if applicable (CP543.5002 initial treatment to CP543.5002 modified treatment):

- CTP-543 8 mg BID
- CTP-543 12 mg BID
- CTP-543 8 mg BID to CTP-543 12 mg BID
- CTP-543 12 mg BID to CTP-543 8 mg BID
- Total CTP-543

For analyses of laboratory evaluations, vital signs, and ECGs, the treatment groups CTP-543 8 mg BID and CTP-543 12 mg BID refer to subjects who initially received CTP-543 8 mg BID or CTP-543 12 mg BID, respectively, during CP543.5002 and received no qualifying dose changes. For clarity, for purposes of identifying treatment groups for these analyses, the initial dose will be the first dose that was dispensed for at least 2 visits; if no dose meets that criteria, then the initial dose is the first dose actually received in CP543.5002. A qualifying dose change is any dose change from the initial dose that spans more than one planned visit in CP543.5002 (i.e., the altered dose was dispensed at two or more consecutive visits). The treatment group CTP-543 8 mg BID to CTP-543 12 mg BID refers to subjects who received a qualifying dose change from 8 mg BID to 12 mg BID during CP543.5002. In the event of more than one qualifying dose change, only the first qualifying dose change will be considered. The treatment group CTP-543 12 mg BID to CTP-543 8 mg BID is defined similarly for qualifying dose changes from 12 mg BID to 8 mg BID.

If there are no subjects with dose adjustments meeting the criteria defined above, the CTP-543 8 mg BID to CTP-543 12 mg BID and CTP-543 12 mg BID to CTP-543 8 mg BID columns may be excluded from summaries which utilize the Safety population.

For analyses of efficacy, subjects will be classified in the same treatment groups as above for laboratory evaluations, vital signs and ECGs:

- CTP-543 8 mg BID

Sun Pharmaceutical Industries, Inc.
Statistical Analysis Plan – CP543.5002

- CTP-543 12 mg BID
- CTP-543 8 mg BID to CTP-543 12 mg BID
- CTP-543 12 mg BID to CTP-543 8 mg BID

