- Total CTP-543

Subjects will further be categorized into “analysis cohorts” based on their prior treatment in the qualifying study (CTP-543 8 mg BID, CTP-543 12 mg BID, or Placebo). Unless otherwise specified in this SAP, efficacy tables will be presented separately by analysis cohort and overall, with treatment groups as columns. If <5 subjects fall under a treatment group for a given analysis cohort, that column will be dropped. All subjects will still be included in the overall column.

Summary tables for exposure, and AEs will include the following treatment columns:

- CTP-543 8 mg BID
- CTP-543 12 mg BID
- Total CTP-543

For analyses of exposure, a subject with a qualifying dose change will be treated as if the subject changed dose from one study to another and will be included under more than one treatment column. For analyses of AEs, AEs will be considered treatment-emergent with respect to the most recent dose taken prior to the start of the adverse event. Subjects may be included in more than one treatment column due to dose changes.

Mock tables and data listings will be provided as attachments to this analysis plan. Minor changes to the mocks after formal SAP approval will not necessitate re-approval unless changes to the text of the SAP are required.

All statistical deliverables will be produced, validated, and reviewed for accuracy/consistency in accordance with [REDACTED] standard operating procedures and the processes described in the statistical validation plan.

SAS® (SAS Institute, Cary, North Carolina) statistical software, version 9.4 or later, will be used for all analyses. Adverse Events and Medical History will be coded in Medical Dictionary for Regulatory Activities (MedDRA) Version 23.1. Concomitant medications will be coded in World Health Organization (WHO) Drug Global Version 2020-SEP and Anatomical-Therapeutic-Chemical (ATC) classification and preferred term.

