9.2. Extent of Exposure

Study drug exposure will be summarized for the CTP-543 8 mg BID and CTP-543 12 mg BID treatment groups and overall. Duration of exposure in weeks will be calculated as (date of last dose of study drug minus the date of first dose of study drug + 1 day)/7. Study drug exposure will be summarized categorically by duration of treatment in weeks ($\geq 4, \geq 8, \geq 12, \geq 16, \geq 20, \geq 24, \geq 28, \geq 36, \geq 44, \geq 52, \geq 60, \geq 68, \geq 76, \geq 84, \geq 92, \geq 100$, and ≥ 108) and will include a summary of subjects receiving ≥ 1 dose. Dose interruptions, missed doses, and partial doses will be ignored. Subjects who are lost to follow-up and were on treatment as of their last visit will be counted as receiving their last dose on the date of the last visit completed. Duration of study drug exposure in weeks as a continuous variable will also be summarized.

All summaries of exposure will be limited to exposure in CP543.5002.

Duration of cumulative study drug exposure in weeks for subjects who entered the OLE will be calculated as (OLE treatment end date – OLE treatment start date – the number of days of missed dose + 1)/7. Duration of cumulative study drug exposure will be summarized and calculated in the same manner as study drug exposure, except that any period of dose interruptions or missed doses will be subtracted. If the reason not dosed is “dose interruption”, it will be counted as a missed dose regardless of the actual number of tablets taken. If the reason not dosed is “missed dose” or “partial dose” and no tablets were taken, it will be treated as a missed dose; if the reason not dosed is “missed dose” but 1 tablet was taken, it will be treated as a partial dose.

Duration of exposure up to a qualifying dose change in CP543.5002 will be summarized as a categorical measure based on treatment sequence between the qualifying study and initial dosing in CP543.5002, as follows: Placebo to 8 mg BID, Placebo to 12 mg BID, 8 mg BID to 8 mg BID, and 12 mg BID to 12 mg BID. Duration of exposure up to a qualifying dose change for subjects previously on placebo will be separately tabulated from that of subjects previously on active drug in the qualifying study. For purposes of these tabulations, if a subject experiences a qualifying dose change, duration of exposure will be counted up to the qualifying dose change. Dose interruptions, missed doses, and partial doses will be ignored.

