Duration of exposure after a qualifying dose change in the OLE study will be summarized as a categorical measure based on treatment sequence for subjects with any qualifying dose change in CP543.5002. The following treatment sequences will be used (based on treatment sequence within CP543.5002): 12 mg BID to 8 mg BID and 8 mg BID to 12 mg BID. For purposes of this tabulation, the relevant duration of exposure will be the last dose of study drug in CP543.5002 minus the date of the first qualifying dose change + 1 day. Therefore, if a subject experiences

more than one qualifying dose change, the subject will be classified according to the first qualifying dose change. Dose interruptions, missed doses, and partial doses will be ignored.

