9.3. Adverse Events

An AE is any untoward medical occurrence that may appear or worsen in a subject during the course of a study. It may be a new intercurrent illness, a worsening concomitant illness, an injury, or any concomitant impairment of the subject's health, including laboratory test values, regardless of etiology. Any worsening (i.e., any clinically significant adverse change in the frequency or intensity of a pre-existing condition) should be considered an AE. A diagnosis or syndrome should be recorded on the AE page of the eCRF rather than the individual signs or symptoms of the diagnosis or syndrome. A worsening of the condition under study, alopecia areata, will not be reported as an AE.

All subjects will be monitored for AEs during the study. Assessments may include monitoring of the following parameters: the subject's clinical symptoms, laboratory, physical examination findings, or findings from other tests and/or procedures.

AEs will be coded using MedDRA version 23.1 and summarized by treatment group, system organ class, and preferred term.

An AE with a start date before the date of the first dose of study drug in CP543.5002 (i.e., generally Day 1), will be considered a pre-treatment AE. TEAEs will be defined as any AE that occurs on or after the day of administration of the first dose of study drug. Non-serious AEs are collected until completion of the study or the Early Termination Visit. Serious adverse events are reported through 30 days beyond the last dose of study drug. The number and percentage of subjects who report TEAEs will be summarized by treatment group, system organ class, and preferred term.

If a subject changes dose during the study, AEs will be considered treatment-emergent with respect to the most recent dose taken prior the start of the AE and will be tabulated under that treatment column. This may result in some subjects being included in more than one treatment column.

TEAEs will also be summarized by intensity as well as relationship to study drug.

Partial dates will be imputed for the purposes of defining TEAEs as follows:

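### Adverse events follow the last dose taken, but exposure follows only qualifying dose changes, so a patient with a single 8 mg dispensing can have 8 mg events and no 8 mg exposure

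*SAP*

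**What the plan says.** SAP 4.1 gives the exposure and adverse event summaries the same three columns: 8 mg BID, 12 mg BID and Total. Neither has a 12-to-8 mg column. The paragraph that follows sets two rules:

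- Exposure: "For analyses of exposure, a subject with a qualifying dose change will be treated as if the subject changed dose from one study to another". Such a patient then appears in more than one column.
- Adverse events: "AEs will be considered treatment-emergent with respect to the most recent dose taken prior to the start of the adverse event". SAP 9.3 repeats this: "If a subject changes dose during the study, AEs will be considered treatment-emergent with respect to the most recent dose taken". The condition is any change of dose; the word qualifying is not used.

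The qualifying change is defined earlier in SAP 4.1, for the laboratory, vital sign and ECG groupings, as one where "the altered dose was dispensed at two or more consecutive visits". SAP 9.2 uses the same trigger in its treatment-sequence tabulations. Before a change, "if a subject experiences a qualifying dose change, duration of exposure will be counted up to the qualifying dose change"; after it, "the relevant duration of exposure will be the last dose of study drug in CP543.5002 minus the date of the first qualifying dose change", plus one day. The main table in SAP 9.2 reports, by dose, the patients with at least one dose and duration rows from 4 to 108 weeks.

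Protocol 11.2 summarises patients as treated, and Protocol 11.2.2 calls for days of exposure by dose. Protocol 11.2 also leaves the definition of dosing regimens to the SAP. SAP 12 lists one departure from the protocol, on laboratory values.

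On supply, Protocol Table 1, footnote 10, says "Study drug dispensation will occur at Visit 9 (Week 52) for RESPONDERS ONLY". Protocol Table 2 shows no dispensing at Week 108.

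**The concern.** The same calendar weeks can count as 8 mg for adverse events and as 12 mg for exposure. The sorting is not neutral, because a second dispensing depends on what happens after the change:

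- A Week 52 non-responder whose first 8 mg supply comes at or after Week 44 gets no second one. An otherwise identical responder does.
- A patient who stops or is withdrawn before the second dispensing never qualifies. Protocol 7.3 requires withdrawal after a thromboembolic event. Such an event after a single 8 mg dispensing would be an 8 mg event in a patient with no 8 mg exposure.
- A one-visit discretionary change, which SAP 7.2 allows in either direction, never qualifies.

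The 12 mg dose was withdrawn after thrombosis reports, so readers will look closely at events near the switch, by dose. SAP 4 bases percentages on the header N of the population summarised, but does not say whether a single-dispensing patient is in the 8 mg N for adverse events. If N were taken from the exposure columns, a patient could be in the numerator and outside the denominator.

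**Working it through.** The plan states no figure for this point, so there is none to reproduce. The check applies both rules to the planned schedule.

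**Inputs.** Dispensing at Weeks 0, 4, 8, 12, 20, 28, 36 and 44 (Protocol Table 1), and for responders also Weeks 52, 60, 68, 76, 84, 92 and 100 (Tables 1 and 2). Treatment ends at Week 52 or Week 108. A change qualifies if at least 2 dispensings of the new dose follow.

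| Patient on 12 mg | First 8 mg supply | Planned 8 mg dispensings | Qualifies | Mismatched weeks |
|---|---|---|---|---|
| Non-responder | Week 36 | 2 | yes | 0 |
| Non-responder | Week 44 | 1 | no | 52 − 44 = 8 (8/52 = 15.4%) |
| Responder | Week 44 | 2 or more | yes | 0 |
| Responder | Week 92 | 2 | yes | 0 |
| Responder | Week 100 | 1 | no | 108 − 100 = 8 (8/108 = 7.4%) |
| Stops before second supply | any | 1 | no | up to about 8 |

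For the second row, the 12 mg column shows 52 weeks instead of 44. The patient is also missing from the 8 mg rows for at least one dose, at least 4 weeks and at least 8 weeks.

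**Who could be in these rows under the urgent safety measure.** SAP 8.2.3.1 dates these reductions on or after 28 Apr 2023. The synopsis estimates the first patient in September 2021 and the last completion in July 2024. Assume that the last completer stays 108 weeks (756 days).

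- Last enrolment: 1 to 31 Jul 2024 minus 756 days = 6 Jun to 6 Jul 2022.
- Position on 28 Apr 2023: Week 46.6 to 42.3 for the last enrolled, Week 82.1 to 86.3 for the first enrolled.
- Weeks 44 to 52 on that date: enrolled 29 Apr to 24 Jun 2022.

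The Week 44 to 52 case is therefore possible. A first 8 mg supply at Week 100 under the measure is not expected, because even the earliest patients still had the Week 92 and Week 100 dispensings ahead.

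**Upper bound for the Week 52 non-responder route.** Assume uniform enrolment from 15 Sep 2021, a prompt switch, 52 weeks per 12 mg patient, and that every 12 mg patient not yet at Week 52 becomes a non-responder.

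- Last enrolment 20 Jun 2022: 52/278 = 18.7% not yet at Week 52. The last patient is at 312/7 = Week 44.6, so 0 to 7.4 weeks remain, mean 3.7. Share of 12 mg time: 0.187 × 3.7/52 = 1.3%; if half are non-responders, 0.7%.
- Last enrolment 6 Jun 2022: (38/264) × 2.71/52 = 0.8%.
- Last enrolment 6 Jul 2022, with those not yet at Week 44 switching at that visit: (56/294) × 4/52 + (12/294) × 8/52 = 1.5% + 0.6% = 2.1%.

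Early stoppers and one-visit changes would add to this. The documents give no number for them.

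**Effect if a reader divides events by exposure.** Assume 100 patients per dose with 52 weeks each, and a share f of 12 mg patients with 8 mismatched weeks. The 8 mg ratio is too high by f × 8/52: 0.8% for f = 5%, 1.5% for 10%, 3.8% for 25%, 7.7% for 50%.

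**An ambiguity in the definition.** SAP 4.1 also describes a qualifying change as one spanning more than one planned visit. If unscheduled supplies do not count, a swap just after Week 36 or Week 92 leaves one planned dispensing and almost 16 mismatched weeks. On the estimated dates no patient was near Week 36 or Week 92 on 28 Apr 2023, so that extreme would come mainly from discretionary changes.

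**The case against.** The case on the other side is substantial, and much of it stands.

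- A reader might infer that planned adverse event rates by dose are biased. They are not: the SAP plans counts and percentages on header N and no exposure-adjusted rate. What is affected is the by-dose exposure table itself, including its count of patients with at least one dose.
- A reader might infer that about 19% of patients are misclassified. That figure is the share of all enrolment not yet at Week 52, under an assumed window. Only 12 mg patients who were also Week 52 non-responders count, and most had less than 8 weeks left.
- A reader might take a comparison of doses to be the first objective. Protocol 6 names the long-term safety of CTP-543 without reference to dose, all summaries are descriptive, and the Total column is unaffected.
- No sentence says that non-qualifying weeks are booked to 12 mg. That follows because exposure is split only for qualifying changes, but it is an inference. The mock tables, which are not in the documents available, might settle it.
- Individual events stay traceable, because the SAP lists all adverse events by subject.
- The SAP may define regimens (Protocol 11.2), and SAP 2 gives the SAP primacy. A minimum-duration filter for brief changes is a defensible convention.

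The last point does not dispose of the matter. The filter applies to exposure alone, nothing reconciles it with the event rule, and SAP 12 does not declare the departure from as-treated exposure by dose.

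**Conclusion.** The inconsistency is real and should be corrected before database lock. Followed as written, two tables with the same columns describe different patient-time for anyone with a single dispensing of the new strength, and later response or withdrawal decides who that is.

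The size is probably small. It is up to about 8 weeks per affected patient if unscheduled supplies count as dispensings, and usually less on the estimated dates. The Week 52 non-responder route accounts for roughly 1% to 2% of 12 mg time as an upper bound, under the enrolment assumptions shown. Most reductions under the urgent safety measure have two or more later dispensings and are split correctly. The number affected cannot be found from the documents.

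The documents do not support the stronger conclusion that planned adverse event results by dose are wrong. Nor do they show a fault in the event rule, which assigns each event to the dose actually being taken.

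**What to change.** In SAP 4.1 and 9.2, for the by-dose exposure table:

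- Split exposure at the actual date of the first dose of the new strength, for every dose change, with no two-visit condition.
- Define the header N of each adverse event dose column as all patients who took at least one dose of that strength.

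Leave the adverse event attribution rule unchanged. Do not align the tables by extending the two-visit condition to events, since that would place an event under a dose the patient was not taking. Keep the qualifying-change rule for laboratory, vital sign, ECG and efficacy groupings and for the treatment-sequence tabulations, and state there whether unscheduled supplies count.

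The cost is SAP wording and reprogramming of some exposure derivations. SAP 9.2 already works with first-dose, last-dose and dose-change dates, so no new data are needed. Some short exposures will appear in the 8 mg column. No patient's treatment changes.

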**Number of patients:**

All patients who participated in a qualifying CTP-543 clinical trial and continue to meet eligibility criteria are eligible to participate.

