**Statistical methods:**

All statistical methods are descriptive. No formal hypothesis will be tested. All confidence intervals, p-values, or any other inferential statistics provided will be exploratory in nature

*Safety Analyses:*

Safety analyses will include all patients who receive study drug. Adverse events will be coded by system organ class and preferred term with the Medical Dictionary for Regulatory Activities. Concomitant medications will be summarized by World Health Organization Drug Dictionary Anatomical-Therapeutic-Chemical classification and preferred term. Adverse events, physical examination findings, electrocardiogram, clinical laboratory information, and concomitant medications will be tabulated and summarized by treatment and dose level. By-patient listings will be provided for any deaths, serious adverse events, and adverse events leading to discontinuation of treatment.

*Efficacy Analyses:*

Efficacy analyses will include all patients who receive study drug and have at least 1 post-baseline SALT assessment in this study. Relative change in SALT score overtime will be summarized descriptively by visit, as appropriate. Additional details for statistical methods will be provided in the Statistical Analysis Plan.

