## 7.3. Patient Withdrawal Criteria

All patients are free to withdraw from participation in the study at any time, for any reason, and without prejudice. The Investigator must withdraw any patient from the study if the patient requests to stop participating in the study. The Investigator, Sponsor, or its designee may remove a patient from the study at any time and for any reason. In addition, patients must be withdrawn if they:

- Have a prior history of thrombotic event(s);
- Experience a thromboembolic event;
- Experience an intolerable adverse event, including but not limited to bone marrow related events characterized by protocol specified hematologic abnormalities, or a  $\geq$  Grade 3 cardiac event, or a  $\geq$  Grade 4 (other) adverse event (CTCAE v5.0 criteria) considered possibly related to study drug. Because laboratory abnormalities can occasionally occur that do not in themselves pose an unacceptable risk to subject safety (e.g., CK elevations with exercise, laboratory errors or artifacts), the occurrence of a  $\geq$  Grade 4 laboratory abnormality, or any laboratory abnormality of concern to the Investigator, will be discussed with the Medical Monitor and a determination will be made, based on a reassessment of risk-benefit for the subject, whether the subject should discontinue randomized treatment. Documentation on the determination will be maintained in the study files;
- Require a medication that is prohibited by the protocol. However, under certain circumstances, and in consultation with the Medical Monitor, short-term use of a

prohibited medication may not necessitate withdrawal when its use is unlikely to unfavorably alter the risk-benefit of subject participation or confound the study endpoints;

- Experience an adverse event of progressive multifocal leukoencephalopathy (PML) or skin cancer which are rare but potential risks of the drug;
- Do not follow guidelines specified in the protocol (i.e., is noncompliant with protocol procedures or study treatment administration);
- In the opinion of the Investigator, have any medically appropriate reason or significant protocol violation;
- Become pregnant;
- Have a serious adverse event associated with a SARS-CoV-2 infection;
- Are lost to follow up;
- Are, in the judgement of the Investigator, not exhibiting clear benefit following one full year of active treatment with CTP-543;

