Following reports of thrombosis with 12 mg BID after long-term administration of CTP-543 and discussions with the US Food and Drug Administration (FDA), the 12 mg BID dose was immediately discontinued and communicated under an Urgent Safety Measure. Due to implementation of this urgent safety measure, all patients previously assigned to the 12 mg BID dose will be dose reduced to the 8 mg BID dose, should they elect to continue in the trial, for the duration of the trial up to a total of 52 weeks for non-responders or a maximum of 108 weeks for responders.

At the Week 52 visit, subjects will be assessed for treatment success (Responders) defined as subjects having an absolute SALT score of ≤ 20 . These Responders will continue in the OLE extension for an additional 52 weeks. Non-responders will complete the study at Week 52. Additionally, subjects should be withdrawn from the study if in the Investigator's opinion

Sun Pharmaceutical Industries, Inc.
Statistical Analysis Plan – CP543.5002

continued study participation is undesirable or the risk-benefit profile has become unfavorable. Additional withdrawal criteria can be found in Section 7.3 of the protocol.

Subject safety will be monitored throughout the study. During the first 12 weeks, hematology, serum chemistry, and lipids will be conducted under fasted conditions every 4 weeks. Following 12 weeks on treatment, subjects will return to the clinic every 8 weeks for safety assessments until the completion of the study or until withdrawal from the study. At each study visit, an assessment should also be undertaken for any changes in the physical exam, or symptoms such as pain, swelling or tenderness in leg(s), persistent breathing difficulties or shortness of breath, or severe headache, that are suggestive of an increased risk of thromboembolism. Patients must be withdrawn if they have a prior history of thrombotic event(s) or experience a thromboembolic event.

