8.2.3.1. Analysis of the Efficacy Endpoint Post-Dose Reduction

[REDACTED]

Subjects with loss of response will be defined as having an absolute SALT score > 50 ; subjects with no loss of response will be defined as having an absolute SALT score ≤ 50 . Responders at pre-dose reduction baseline will be defined as having an absolute SALT score ≤ 20 at pre-dose reduction baseline; non-responders will be defined as having an absolute SALT score > 20 . A line graph of the absolute change from pre-dose reduction baseline SALT score vs. visits since dose reduction will also be produced for subjects who had a dose reduction from CTP-543 12 mg to 8 mg on or after 28 Apr 2023 due to the urgent safety measures.

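### The adverse event tables set 8 mg time from before and after the urgent safety measure beside 12 mg time that is essentially all before it, with no cut at that date

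*SAP*

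**What the plan says.** SAP 4.1 gives exposure and adverse events three columns: 8 mg, 12 mg and Total. Events are placed by the rule "AEs will be considered treatment-emergent with respect to the most recent dose taken prior to the start of the adverse event", and a subject whose dose changes can appear in two columns. SAP 9.3 repeats this. Its summaries are counts and percentages of subjects plus numbers of events, and SAP 4 makes the column N the default denominator. SAP 9.1 to 9.4 contain no calendar cut and no exposure-adjusted rate.

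SAP 3 says that, after thrombosis reports, "the 12 mg BID dose was immediately discontinued and communicated under an Urgent Safety Measure" and that "all patients previously assigned to the 12 mg BID dose will be dose reduced to the 8 mg BID dose" if they choose to stay, for up to 52 weeks (non-responders) or 108 weeks (responders).

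A date for the measure appears only in the efficacy section. SAP 8.2.3.1, partly redacted, plans a graph for subjects with a "dose reduction from CTP-543 12 mg to 8 mg on or after 28 Apr 2023 due to the urgent safety measures". SAP 9.2 divides exposure before and after a qualifying dose change. Nothing similar is planned for adverse events.

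The current text also asks at every visit about findings "that are suggestive of an increased risk of thromboembolism", and requires withdrawal of patients with a thrombotic history or event (Protocol 6.1 and 7.3). Neither rule carries an effective date.

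**The concern.** The two dose columns do not cover the same calendar period. Patients who took 8 mg throughout contribute time on both sides of the measure, and former 12 mg patients add further 8 mg time after it. The 12 mg column stops at about the measure. Choosing a column for events after a dose reduction does not cure this, because patients who never changed dose also span both periods.

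Anything that altered the recording or the true risk of events around that date acts on 8 mg almost alone. Closer questioning or greater awareness would raise recorded leg pain, breathlessness, headache and thrombosis. Withdrawing at-risk patients would lower events. Any delayed effect of earlier 12 mg dosing would also be counted under 8 mg.

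Long-term safety is a stated objective, and 12 mg was stopped because of thrombosis reports. Readers will look from one column to the other on exactly those events.

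**Working it through.** The plan gives no sample size or event figure to reproduce; enrolment is open-ended ("All patients who participated in a qualifying CTP-543 clinical trial and continue to meet eligibility criteria are eligible to participate"). The check is calendar arithmetic followed by an illustrative split of patient time.

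**Inputs from the documents.** Estimated first enrolment September 2021 and last completion July 2024 (Protocol synopsis). Maximum treatment 52 or 108 weeks. Reductions from 28 Apr 2023 (SAP 8.2.3.1).

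**Assumptions, not in the documents.** Uniform entry from 1 Sep 2021 to 20 Jun 2022 (15 Jul 2024 minus 108 weeks). Equal numbers starting each dose. The same 30-70% responding at Week 52 on both doses. 50-100% of 12 mg patients on study continuing at 8 mg. No other drop-out and no 12 mg dosing after the date. The visible text does not say when the Week 52 exit for non-responders began, so it is applied either throughout or only from the measure.

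**Study week at the measure.** From 1 Sep 2021 to 28 Apr 2023 is 604 days, or 86.3 weeks. From 20 Jun 2022 it is 312 days, or 44.6 weeks. So t runs from 44.6 to 86.3, a span of 41.7 weeks with mean 65.4.

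**Mean weeks per starter**, with before = min(D, t) and after = max(D - t, 0):
- Responders (D = 108): before 65.43; after 108 - 65.43 = 42.57.
- Non-responders (D = 52): after (52 - 44.57)² / (2 × 41.71) = 0.66; before 52 - 0.66 = 51.34, or 65.43 if the exit applied only from the measure.

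**Share of 8 mg time after 28 Apr 2023.** With c the fraction of 12 mg patients continuing, the column share is f = after × (1 + c) / [before + after × (1 + c)].

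| | Low end | High end |
|---|---|---|
| Responders; exit rule; c | 30%; from the measure; 0.5 | 70%; throughout; 1.0 |
| Before | 65.4 | 0.3 × 51.34 + 0.7 × 65.43 = 61.2 |
| After | 0.7 × 0.66 + 0.3 × 42.57 = 13.2 | 0.3 × 0.66 + 0.7 × 42.57 = 30.0 |
| 8 mg starters only | 13.2 / 78.6 = 17% | 30.0 / 91.2 = 33% |
| Whole 8 mg column (f) | 19.8 / 85.2 = 23% | 60.0 / 121.2 = 50% |
| 12 mg column | about 0% | about 0% |

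A second set of assumptions (entry to 6 Jul 2022, 30-80% responding, 70-100% continuing, exit rule throughout) gives f of 30-53%.

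**Effect on a rate comparison.** Suppose true rates are equal and recorded events after the measure are multiplied by k. The apparent 12 mg to 8 mg rate ratio is 1 / [(1 - f) + f × k].

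| k (illustrative) | f = 0.23 | f = 0.50 |
|---|---|---|
| 2 | 1/1.23 = 0.81 | 1/1.50 = 0.67 |
| 1.5 | 1/1.115 = 0.90 | 1/1.25 = 0.80 |
| 0.5 | 1/0.885 = 1.13 | 1/0.75 = 1.33 |

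With a cut at the date, f = 0 and the ratio is 1.00 for any k.

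**Effect of the column-N denominator.** This arises even with k = 1. Take N for 8 mg as everyone who ever took 8 mg. The share of 12 mg starters still on study at the measure is all responders plus (52 - 44.57)/41.71 = 17.8% of non-responders: 0.425 at 30% response and 0.753 at 70%. Weeks per subject, 8 mg against 12 mg:
- 70% responding, exit throughout, c = 0.5: (61.2 + 45.0) / 1.377 = 77.1 against 61.2, ratio 1.26.
- 30% responding, exit from the measure, c = 1: (65.4 + 26.4) / 1.425 = 64.4 against 65.4, ratio 0.98.

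For uncommon events, crude percentages at equal true rates would differ by about these factors.

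**The case against.** The strongest objection concerns the rule change. A reader might infer that thromboembolism surveillance and withdrawal rules changed at the measure, so that detection differs by dose. The documents do not show this. The visit screen and the withdrawal criteria are undated, and no earlier protocol text is visible. SAP 3 says the discontinuation was communicated, without naming recipients or content. Listing prior thrombosis as both an exclusion example (7.2) and a withdrawal reason (7.3) hints at a later addition, but if the exclusion applied at entry, few such patients would remain to remove. The one dated text, Protocol 8.1.1, cites January 2023 and directs withdrawal of increased-risk patients. A change made then could precede the measure and touch both doses. This objection stands: the change in ascertainment is conditional. It does not make the cut misplaced, since both doses ran concurrently up to the measure and an earlier change would fall within the same calendar window for both columns.

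Next, no dose comparison is planned: "All statistical methods are descriptive. No formal hypothesis will be tested". That is true, but adjacent columns by dose will be compared anyway.

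Third, there are partial safeguards: a late-2022 data freeze, by-subject listings with treatment-emergent events flagged, and exposure split at dose changes. The freeze feeds integrated summaries under separate SAPs (SAP 8.1.2 and 11), and none of these provides an event table for this study over a common period.

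Finally, 28 Apr 2023 is a selection date worded as on or after, so some 12 mg time may lie beyond it. That also stands, and is why the 12 mg share is given as about 0%.

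**Conclusion.** The structural point holds on the documents' own text. The 8 mg column pools time before and after the measure, the 12 mg column is essentially all before it, percentages use column N, and nothing is cut at the date. Dose is partly confounded with calendar period and follow-up length. The confounding is not complete, because the doses overlapped until the measure.

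The imbalance is about 23-50% of 8 mg column time against about 0% of 12 mg time, resting on the entry, response and continuation assumptions above. The effect on an event contrast depends on an unknown change in recording or risk. The illustrative ratios run from 0.67 to 1.33 around a true 1.00, so neither direction nor size of bias is established.

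A second tempting inference is that tables restricted to the earlier period would be a clean dose comparison. They would share a calendar window, but the study is open-label, and only former placebo patients were randomised within it (SAP 7.2); the others kept their parent-trial dose.

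SAP 7.2 also still permits changes to 12 mg at the investigator's discretion, while SAP 3 says that dose was discontinued. The two sections must be reconciled.

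**What to change.** In SAP 9.3:
- Add the overall treatment-emergent summary and the system organ class and preferred term table, restricted to onset before 28 Apr 2023, for 8 mg and 12 mg. Cut exposure at the same date and give exposure-adjusted rates.
- Tabulate 8 mg events from that date onward separately, and list any 12 mg time or events on or after it.
- State that the whole-study columns should not be read as a dose comparison. Describe the earlier-period tables as the like-for-like calendar comparison, open-label and randomised within this study only for former placebo patients.
- State when the thromboembolism screen and withdrawal rules took effect, so readers can judge whether ascertainment changed.
- Reconcile SAP 7.2 with SAP 3 on dose changes.

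The cost is SAP wording and two or three repeat tables using a date the SAP already holds. The downside is fewer 8 mg events in the comparison table.
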